### **3. PRELIMINARY RESULTS:**

Our preliminary results are shown in the work entitled “**Low zinc levels at clinical admission associates with poor outcomes in COVID-19**” (13) which is the result of a tight collaboration between the laboratory of [name] (Hospital del Mar) and those of [name] and [name] (both at DCEXS, UPF).

This work aimed to focus clinical attention on serum zinc content (SZC) in COVID-19 patients. Our analysis showed a robust correlation between low SZC with COVID-19

severity and mortality. The cause is likely to be a combination of immune system imbalance and a direct benefit of viral replication.

A summary of the results obtained:

- In our retrospective observational study with 249 COVID-19 patients, **23% of the patients had at admission SZC lower than 50µg/dl**, the cutoff associated with ZD and development of clinical signs.
- Our study showed that **low SZC correlates with higher IL-6 and C-reactive protein at admission**, higher peak IL-6 during the episode.
- We detected in the low SZC group that subjects needed higher time to recover (25 days) versus the control group (8 days). In the same direction, the **mortality in low SZC patients was higher (21%) than in the control group (5%)** with normal zinc concentration.
- **SARS-CoV2** Infections in cell culture demonstrated that **low zinc levels favors SARS-CoV2 viral expansion** in the infected cells.

These results highlighted the urgent need to start clinical trials supplementing with zinc low SZC patients at admission to reestablish zinc homeostasis in order to study the cause-effect association between zinc nutritional status and COVID-19 progression. We expect with this new project that zinc supplementation in low SZC COVID-19 patients will

balance what has been called the cytokine storm caused by SARS-CoV-2 and as a consequence will reduce COVID-19 severity and mortality.

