### **Study Endpoints**

#### **Primary Endpoints**

- Number of days since admissions to clinical recovery
- Change in IL-6 levels from baseline to Week 2.
- Percentage of patients with disease progression by Week 2 based on WHO 9-point ordinal scale

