### **Task 1.1.1 Visits and sample collection**

1.- Visit 1. Screening. Randomization. Baseline. Phase / Visit 0 or 1 ( Day 1 or up to 1 day  
Prior to Baseline/Randomization; In Person)

Visit performed at admission (+1). Written informed consent obtained. Medical history.  
Vital signs assignment. Clinical labs (CBC, CMP, CRP, ferritin, D-dimer,IL-6, zinc)

2.-Visit 2 / Week 1 (Day 7  $\pm$  2 days)

A complete record of AEs and concomitant therapies will be taken into account. 3.-

Visit 3 / Week 2 (Day 14  $\pm$  2 days), End of Treatment

A complete vital sign assessment (sitting blood pressure, heart rate, respiratory rate, O2  
sat, and oral temperature) review and record AEs and concomitant therapies, clinical  
labs (stated above) and PBMCs. Collect blood samples for future studies.

4.-Visit 4 / End of Study (Day 28  $\pm$  4 days)

Clinical labs (stated above) and PBMCs. Collect blood samples for future studies.

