### **Statistical analysis**

**Randomization: Subjects** will be randomized in a 1:1 ratio to:

- 83.91 mg zinc acetate (Zinc+NM) QD + standard of care for 2 weeks
- Standard of care for 2 weeks

**Determination of sample Size:** Sample size calculations are aimed at comparisons of days to clinical recovery between zinc supplementation and standard of care alone. Assuming alpha = 0.05 and a 10% dropout rate, randomization of 60 subjects will

provide 80% power to detect a difference in time to recovery between arms of 3 days assuming a SD of 4 days. This sample size will also provide at least 80% power to detect a change in percentage of people with clinical progression of 5% based on an estimated

clinical progression rate of 20% in the standard of care arm.

**Analysis Populations:** The analysis population for efficacy will be per protocol which includes all randomized subjects who complete 2 weeks of therapy and/or return for Week 2 visit. All safety analyses will include all randomized subjects who are

administrated at least 1 packet of the investigational product.

**Baseline Characteristics:** Demographics and Baseline characteristics will be summarized descriptively by group and overall using per protocol population. The following Baseline

characteristics will be summarized: sex, race, age, comorbidities, ethnicity

**Clinical Laboratory Assessments:** Blood chemistry, hematology parameters will be summarized at Baseline as well as visit 3 and 4. Laboratory values at Baseline and subsequent changes in laboratory values will be summarized descriptively overall and

by therapy group.

**Vital signs:** Vital sign measurements will be summarized at Baseline, Week 2 and Week 4. In addition, changes from Baseline to Week 2 or 4 will be summarized. For each summary the number, mean, median, standard deviation, minimum, and maximum

values will be presented overall and by therapy group.

**Safety Analyses:** All safety analyses will be based on the Safety Population, comprising all subjects who are randomized to the therapy group and subsequently receive at least one packet of investigational product. Safety assessments will be analyzed by frequency of events/abnormalities for categorical values or summarized using descriptive statistics

(mean, standard deviation, median, range, and number of observations).

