**Adverse events:** Adverse events will be coded using the Medical Dictionary for Regulatory Activities (MedDRA) coding dictionary. Adverse events will be defined as any event with a start date occurring on or after initiation of therapy on Day 1 or, if pre-existing, worsening after initiation of therapy on Day 1. The incidence of AEs will be

summarized by body system and MedDRA preferred term, overall and by therapy group.

If a subject reports the same AE more than once, then that subject will only be counted once for the summary of that AE, using the most severe intensity.

**Handling of Dropouts or Missing Data :** Dropouts or participants missing data for the primary endpoints will be excluded from the analysis.

**Limitation:** We might find no benefit in COVID-19 patients supplemented with zinc. That would mean that the low zinc levels detected in COVID-19 patients with worse prognosis are a consequence of the inflammatory status. The results will be also very helpful for physicians worldwide.

- **To study the immune responses of the COVID-19 patients enrolled in the clinical trial (Subproject 2)**

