### **3 To characterize novel zinc homeostasis reporters upon SARS-CoV2 infection**

**(Subproject 2)** We will run RT-PCR for the 14 Zip and 10 ZnT transporters and for MT1 and MT2. The expression analysis will be correlated to serum zinc levels measured.

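### A null result cannot show that low zinc is a consequence of inflammation, and baseline serum zinc is collected but has no named role in any efficacy analysis

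*Combined protocol and SAP*

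**What the plan says.** All references are to the combined protocol and SAP.

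- **Reading of a null.** The limitation paragraph of the Statistical analysis section considers the possibility of no benefit and says: "That would mean that the low zinc levels detected in COVID-19 patients with worse prognosis are a consequence of the inflammatory status". It offers no other explanation.
- **Where benefit is expected.** The Preliminary Results section argues for an "urgent need to start clinical trials supplementing with zinc low SZC patients at admission" and expects the gain in such patients. It reports that 23% of the earlier 249-patient cohort were below 50 µg/dl at admission. Time to recovery was 25 days in the low-zinc group and 8 days in the control group.
- **Who is enrolled.** The inclusion and exclusion criteria contain no zinc threshold. Patients "will be randomized in a 1:1 ratio to" the two arms, and no stratification is stated.
- **What is measured.** Task 1.1.1 lists at Visit 1: "Clinical labs (CBC, CMP, CRP, ferritin, D-dimer,IL-6, zinc".
- **How it is used.** IL-6 enters efficacy through a primary endpoint, "Change in IL-6 levels from baseline to Week 2". Otherwise, "Laboratory values at Baseline and subsequent changes in laboratory values will be summarized descriptively overall and" by therapy group. The listed baseline "characteristics will be summarized: sex, race, age, comorbidities, ethnicity" do not include zinc. The only other stated use of serum zinc is mechanistic: under objective 3, "The expression analysis will be correlated to serum zinc levels measured".
- **Model.** No test or model is named for any efficacy endpoint.

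**The concern.** Whether low zinc drives poor outcome or merely reflects inflammation is the question that the project says is open. The limitation paragraph settles it in advance from a non-significant comparison. Three features of the documents stand against that reading.

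1. The trial tests supplementation in all comers, while the hypothesis concerns a minority of them.
2. The sample is small, so absence of significance is weak evidence of absence of effect.
3. The Background section describes both directions at once: IL-6 lowering available zinc, and zinc lowering IL-6 production. It also ties benefit in the common cold to starting within 24 hours of symptoms. A null after treatment from admission is compatible with several explanations.

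The listed deliverable is a treatment guideline, and the paragraph itself expects a null result to be useful to physicians worldwide. A mistaken reading would therefore travel.

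The second issue is one of efficiency. The sponsor's own data suggest that recovery time differs widely by zinc status, yet the zinc value already collected plays no part in the treatment comparison.

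**Working it through.** **Inputs from the documents.** 60 randomised 1:1, 10% dropout (54 analysed, 27 per arm), alpha 0.05 (two-sided assumed), difference 3 days, SD 4 days, control progression rate 20%, change 5 points (Statistical analysis). Low-zinc share 23%, recovery 25 and 8 days (Preliminary Results).

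**1. The plan's own recovery figure.** SE = 4 × √(2/27) = 1.089. Power = Φ(3/1.089 − 1.96) = Φ(0.796) = 0.787. With 30 per arm it is 0.828. The stated 80% reproduces.

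**2. The plan's progression figure.** For 20% against 15%, power is 0.069 at 27 per arm and 0.073 at 30 per arm. Eighty per cent power would need about 906 per arm. The stated figure of at least 80% does not reproduce. For 20% against 25%, power is 0.064 to 0.067.

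**3. Dilution.** Expected low-zinc patients: 0.23 × 60 = 13.8 randomised (binomial 95% range 8 to 20) and 0.23 × 54 = 12.4 analysed, so 6 to 7 per arm. If only they benefit, the average effect is 0.23 times their benefit. Power at SD 4:

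| Benefit in low-zinc patients | Average effect | Power, 27 / 30 per arm |
|---|---|---|
| 3 days | 0.69 days | 9.2% / 9.8% |
| 6 days | 1.38 days | 24% / 27% |

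An average of 3 days would need 3/0.23 = 13.0 days in the low-zinc patients.

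**4. What a null would leave open.** The 95% CI half-width for the recovery difference at 27 per arm is 2.007 × 1.089 = 2.2 days, so a non-significant result could leave a benefit of 2 days or more unexcluded.

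**5. Size of the zinc signal.** Treating 25 and 8 days as means, chance imbalance in the low-zinc share shifts the arm difference with SE 17 × √(0.23 × 0.77 × 2/30) = 1.85 days (1.95 at 27 per arm).

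**6. Power from adjustment (simulation, illustrative).** 27 per arm, 23% low zinc, uniform 3-day effect, equal SD within both zinc groups. The linear column assumes normally distributed zinc with a step in recovery at the 23rd percentile.

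| Gap, within-group SD | Unadjusted | Indicator below cutoff | Zinc entered linearly |
|---|---|---|---|
| 17 days, SD 4 | 26% | 76% | about 38% |
| 17 days, SD 6 | 21% | 43% | about 28% |
| 17 days, SD 8 | 17% | 26% | about 21% |
| 8.5 days, SD 4 | 52% | 76% | not tabulated |

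**7. Zinc-specific effects.** Power for 3 days within the low-zinc group is about 22% to 29%. For a 3-day interaction, SE = 4 × √(2/6.21 + 2/20.79) = 2.59 and power is about 21%.

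**8. IL-6.** With equal variances at baseline and Week 2 and correlation rho, the ratio of ANCOVA variance to change-score variance is (1 − rho²)/(2(1 − rho)) = (1 + rho)/2. That is 0.65 at rho 0.3 and 0.75 at rho 0.5. The documents give no rho; these values are assumed.

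**The case against.** **The sentence is a remark, not a rule.** It sits in a one-line limitation, triggers no analysis, and the project has a separate mouse experiment aimed at causality. That is fair, and a reader should not infer that the plan claims proof or that the conclusion is false. The documents show only that it would be unsupported. But the sentence rests on the trial result alone, so the mouse work does not repair it.

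**Zinc and IL-6 are not ignored.** A reader might infer that neither baseline value is used. That goes too far: baseline IL-6 is the reference of a primary endpoint, and serum zinc is correlated with gene expression. What stands is narrower. Zinc has no role in an efficacy analysis, and IL-6 is not named as a covariate.

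**Zinc is not shown to be the strongest predictor.** No section ranks predictors, and the Background section reports that zinc and IL-6 were both robustly associated with progression.

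**The power gain is fragile.** The rise from 26% to 76% needs the binary term, equal SDs, and 25 and 8 days taken as means, which the text does not state. It also ignores deaths (21% mortality in low-zinc patients in the earlier cohort) and assumes a uniform effect. With a 3-day benefit in low-zinc patients only, adjusted power at SD 4 is about 9%. The plan's SD of 4 is for recovery time overall. A 17-day gap at 23% alone implies 17 × √(0.23 × 0.77) = 7.2 days, so part of the contrast is really a question about the planning SD. All of this stands, so the gain is illustrative.

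**Change scores are valid.** Under randomisation they are unbiased, and ANCOVA is an efficiency gain rather than a correction. That stands too.

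**Conclusion.** The point holds in two parts.

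The inference from a null to reverse causation is wrong as written. With 23% low-zinc patients and benefit confined to them, a 3-day benefit has about 10% power and a 6-day benefit about 24% to 27% at SD 4. The stated progression change has about 7% power whatever the zinc mix. These figures rest on the earlier cohort's 23% and the plan's SD. A null is not inevitable: a benefit near 13 days in low-zinc patients would restore the planned average effect. Even so, a null would not by itself fix the direction of causation.

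Leaving baseline zinc out of the efficacy analyses is a missed, nearly free improvement rather than an error. Its value depends on the form chosen and on assumptions that the documents cannot confirm. A zinc subgroup would not make a null conclusive, because 6 to 7 low-zinc patients per arm allow only exploratory estimates.

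**What to change.** 1. Replace the sentence in the limitation paragraph with: *A non-significant result will be reported as an estimate with 95% CI and will not be taken as evidence that low zinc is a consequence of inflammation.*
2. Pre-specify baseline zinc as a covariate in the recovery analysis, in a stated form: an indicator for below 50 µg/dl, the cutoff already used in the Preliminary Results section.
3. Analyse log IL-6 at Week 2 by ANCOVA on log baseline IL-6.
4. Report the treatment effect below 50 µg/dl and the zinc-by-treatment interaction as exploratory estimates with CIs, without tests of significance.
5. Keep any zinc adjustment of the progression endpoint secondary. At a 20% rate only 0.20 × 54 ≈ 11 events are expected, too few for stable covariate modelling.

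The cost is analysis wording and one or two degrees of freedom. Both values are already collected at Visit 1, so no visit, sample or recruitment change is needed. The choices should be fixed before outcome data are seen.

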#### **Task 1.2.1 Assessment of B-cell responses in COVID-19 patients**

We will use sera samples from COVID-19 patients enrolled in the clinical trial described in objective 1.1 in both groups. We will measure antibody production against SARS-CoV2 virus at admission, 2 weeks and 28 days post admission. We will carry out ELISA experiments to measure IgM, IgA, IgG1 and IgG2a immunoglobulins against recombinant SARS-CoV2 spike protein.

#### **Task 1.2.2 Assessment of antiviral T-cell responses in COVID-19 patients**

We will use PBMC from COVID-19 patients enrolled in the clinical trial described in objective 1.1 in both groups. We will evaluate T cell responses using intracellular staining and flow cytometry. Subtype population (CD3, CD4, CD8), activation degree (IL-2, INF $\gamma$ , perforin), exhaustion (PD-1, Tim-3) and memory (CD45RO and CD62L) markers will be evaluated using panels of tagged antibodies. We will stimulate T-cells using a commercial pool of overlapping spike peptides of SARS-CoV2. We will study activation degree and exhaustion at admission and at 2 weeks. We will evaluate memory at 28 days post admission.

**EO:** We expect to know whether zinc supplements might strengthen humoral and cellular adaptive immunity in COVID-19 patients. This will be of special interest for immunologists and pharma companies

**D2:** Publication describing the results obtained in the clinical trial with COVID-19 patients and the influence of zinc supplementation in their immune response

## **2. To establish causal-effect associations between Zn levels and SARS-CoV-2 infections (Subproject 3)**

### **Task 2.1 To monitor SARS-CoV-2 infection progression in susceptible mice with different Zn supplementations.**

We will use as an infection model our own colony of transgenic mice expressing human ACE2 (K18-hACE2). Animals will be fed with different supplemented zinc diets (Research diets Inc, or similar). Groups of mice (n=21) will be fed with standard diet, zinc deficiency (ZD) diet (10mg Zn/kg), adequate (AD) diet (30mg Zn/kg) and supplemented (SD) diet (150 mg Zn/kg) for 30d before infection to the end of the experiments. Zn levels in the serum of mice will be determined before challenge with infectious virus. Mice will be anesthetized and intranasally challenged with a lethal dose of a Spanish SARS-CoV-2 D614G(S) isolate and followed for 3 weeks.

Evaluation will be performed by assessing the mice's clinical health score (appearance, mobility and alertness, body weight and temperature) and mortality rates after being challenged with SARS-CoV-2 following standardized guidelines. Mice will be bled at different times post-infection and the viremia will also be compared between different treatments.

### **Determination of sample size**

Group size was calculated according to the equation in (PMID: 24250214) for quantitative endpoint data in order to detect a significant 45% change in survival and considering a 5% of significance level ( $P < 0.05$ ) and 80% power of the analyses.

### **Task 2.2 To study impact of zinc nutritional status on adaptive immune responses against SARS-CoV2**

Groups of K18-hACE2 mice ( $n=30$ ) will be fed and challenged as in task 2.1. Ten mice/group will be anesthetized and sacrificed 7, 15, and 21 d.pi., and spleen and PBMC will be used. T-cell responses will be evaluated using intracellular staining and flow cytometry. Subtype population ( CD4, CD8, ...), activation degree (IL-2, INF $\gamma$ , perforin), exhaustion (PD-1, Tim-3) and memory (CD45R0, CD44m cd103a, CD62L) markers will be evaluated using panels of tagged antibodies. We will stimulate T-cells using a commercial pool of overlapping spike peptides of SARS-CoV2. Antibodies against SARS- CoV-2 elicited in sacrificed mice will be also evaluated by ELISA to compare humoral immune response.

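### Task 2.2 gives 30 more mice per diet the same feeding and lethal challenge but states no survival use of them; a task-stratified survival analysis of both tasks would add power without extra animals

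*Combined protocol and SAP*

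**What the plan says.** Task 2.1 lists four diets with 21 mice each (n = 21 is read as per diet). The mice are "challenged with a lethal dose of a Spanish SARS-CoV-2 D614G(S) isolate and followed for 3 weeks". Its readouts are a clinical health score, serial bleeds for viremia, and "mortality rates after being challenged with SARS-CoV-2 following standardized guidelines". The sample size section that follows sets the group size "for quantitative endpoint data in order to detect a significant 45% change in survival", "considering a 5% of significance level ( $P < 0.05$ ) and 80% power of the analyses". It gives no reference survival and no SD, and does not say whether the 45% is absolute or relative.

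Task 2.2 uses 30 mice per group that "will be fed and challenged as in task 2.1. Ten mice/group will be anesthetized and sacrificed 7, 15, and 21" days after infection. Its readouts are T-cell markers and antibodies, and it is sized by Lehr's formula on CD4+ T-cell fluorescence intensity (MFI).

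Neither task names a survival test or a survival analysis set. Task 2.2 does not say how mice are allocated to sacrifice days, or how a death before the scheduled day is handled.

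**The concern.** Each diet has 21 + 30 = 51 mice given the same feeding and challenge, and a survival use is stated for 21 of them. A Task 2.2 mouse is at risk of death from challenge until its sacrifice. If its sacrifice day does not depend on its health, that follow-up is ordinary right-censored survival data.

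The single expected outcome stated after both tasks is whether zinc status before infection determines progression, and the linked deliverable is a communication to physicians and public health decision makers on prophylaxis. Survival bears directly on that. If deaths in Task 2.2 are not logged, or sacrifice days are chosen by how the mice look, the information cannot be recovered later.

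**Working it through.** **1. The plan's own figures.**

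Task 2.2: Lehr's formula gives n = 16/(13/10)² = 16/1.69 = 9.47, so 10 per group per time point, and 3 × 10 = 30. This reproduces, and it supports reading 30 as per diet, all of them used by the three sacrifice days.

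Task 2.1: 21 cannot be strictly reproduced, because neither an SD nor a reference survival is given. Two-sided 5% is assumed.
- Two means, n = 2(1.960 + 0.842)² SD²/45². With SD = 50 points (the largest for a yes/no outcome), n = 19.4, so 20, or 21 with the t-based version. With SD = 52, n = 20.96, so 21.
- Two proportions, absolute 45-point difference: 13 to 19 per group depending on the reference rate, or 17 to 23 with continuity correction.

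So 21 is consistent with the stated inputs on an absolute reading.

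**2. Power of Task 2.1 alone at the planned effect.** For 72.5% vs 27.5% mortality, with the pooled two-proportion formula:
- SE under the null = √(2 × 0.5 × 0.5/21) = 0.1543
- SE under the alternative = √(2 × 0.275 × 0.725/21) = 0.1378
- z = (0.45 − 1.960 × 0.1543)/0.1378 = 1.07, so power is about 86%

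Other reference rates give up to about 97%. The 80% target is met. With Bonferroni over all six pairs of four diets (an assumption; the plan names no adjustment), power falls to about 62–84%.

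**3. How much follow-up Task 2.2 adds.** Ten mice per diet leave at day 7 and ten at day 15, so only 21 + 10 = 31 of 51 are scheduled to day 21. At 72.5% vs 27.5% mortality, expected deaths in a two-diet comparison equal the number of fully followed mice per diet, because the two rates add to 1.
- Task 2.1 alone: 21.
- Both tasks, all deaths by day 7: 21 + 30 = 51.
- Both tasks, deaths even over days 1–21: 21 + 10 × 7/21 + 10 × 15/21 + 10 = 41.5.
- Both tasks, all deaths on days 16–21: 21 + 10 = 31.

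Task 2.2 is therefore worth about 10 to 30 fully followed mice per diet. Task 2.1 supplies between 21/51 = 41% and 21/31 = 68% of the expected deaths.

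**4. Power with both tasks.** Simulated log-rank test, two-sided 5%, one pair of diets, stratified by task, Task 2.2 mice censored at day 7, 15 or 21 (10 each), 3,000 runs per scenario. Mortality levels and death days are assumptions.

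| Mortality | Task 2.1 alone | Both, deaths d4–7 | Both, d5–10 | Both, d8–14 | Both, d1–21 | Both, d16–21 |
|---|---|---|---|---|---|---|
| 72.5% vs 27.5% | 84% | 99.6% | 99% | 98% | 98% | 95% |
| 100% vs 55% | 92–94% | 100% | 99.7% | 99.7% | 99.5% | 99% |
| 72.5% vs 42.5% | 48–49% | 86% | 79% | 77% | 72% | 65% |
| 95% vs 70% | 44–46% | 81% | 74% | 73% | 66% | 61% |

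Over the wider set of 30-point scenarios tried (including 65% vs 35%), power rises from roughly 45–58% to 64–87%. With equal mortality, the rejection rate stays near 5%.

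**The case against.** **Silence is not exclusion.** A reader might infer that the plan discards the Task 2.2 mice or treats their early deaths as lost animals. The documents support neither reading: no survival analysis set is defined, and such deaths are neither included nor excluded. What stands is that no survival use is stated.

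**Task 2.1 is adequately sized for its own target.** This stands for an absolute 45-point difference. Sizing each experiment for its own endpoint is a defensible design, and the smaller effects in the table are ones the plan did not set out to detect. The point is therefore an improvement, not a correction.

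**The headcount flatters the gain.** It is tempting to say that 59% of the data (30/51) go unused. That counts animals, not information: 20 of the 30 are removed by day 15. A simple day-21 mortality proportion could not use those 20 at all, so the gain needs a time-to-event analysis.

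**Pooling may not be valid.** The task gives sacrifice days and counts but no allocation rule. Filling each day with ten mice picked by condition would make the censoring informative. Task 2.1 mice are also bled repeatedly, and no serial bleeding is stated for Task 2.2. Both objections stand against naive pooling. Setting the sacrifice day independently of health answers the first, and stratifying by task answers the second.

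**It is a mouse subproject.** True: nothing here touches trial participants or the trial's endpoints.

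**Conclusion.** The point holds as a cheap efficiency gain. Recording and using deaths before sacrifice in Task 2.2 raised power in every scenario tried. The gain is modest at the planned effect, where power is already above 80%. It is substantial for differences of 25 to 30 points, where Task 2.1 alone has about even odds or less in most scenarios, and useful if several diets are compared with adjustment.

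The size rests on assumed mortality levels and death days, a two-sided 5% test and an absolute reading of the 45%. On a relative reading the adequacy of 21 depends on the reference rate: a 45% relative drop from 80% survival would need 28 per group. The gain is smallest if deaths come late and largest if they come within the first week. Valid pooling also requires sacrifice days unrelated to health, which the plan does not yet state.

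**What to change.** Keep Task 2.1 as the sized survival comparison. Add to Tasks 2.1 and 2.2 that survival is also analysed across both tasks by log-rank or Cox, stratified by task, with Task 2.2 mice censored at scheduled sacrifice and every earlier death recorded as an event, using the same definition of death in both tasks. State how the sacrifice day is set: either assigned at random before challenge, or by drawing at random from the live mice on the day.

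Cost: no extra animals or procedures, a death log in Task 2.2, a randomisation step and one analysis sentence. The real downside is for the immune readouts. All 30 mice are committed to the three days with no allowance for deaths, so after a lethal challenge some time points may have fewer than 10 live mice. Drawing from live mice on the day shifts that shortage to the later time points but does not remove it. The plan should say that such shortfalls are accepted and reported, and not filled by selecting mice on condition.

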## Sample size

Group size was calculated using Lehr's formula to have a power of 80%, considering a 5% level of significance, and a difference of 13 MFI in the CD4+ T cells between the two group means and assuming a combined standard deviation of 10 MFI (PMID: 18341999).

**EO:** We expect to answer the question whether zinc nutritional status before SARS-CoV2 infection determines COVID-19 progression. Moreover, we expect to understand the correlation between serum zinc levels and disease progression.

**D3:** Scientific communication addressed to physicians and public health decision makers describing the potential benefits of using zinc supplementation as a prophylactic strategy against severe COVID-19.

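### Task 2.2 (mice): the 80% power holds only if almost no animal dies before its sampling day after a lethal challenge, and comparisons made after deaths begin are among survivors

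*Combined protocol and SAP*

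**What the plan says.** Task 2.2 sets the number of animals and the challenge: "Groups of K18-hACE2 mice ( $n=30$ ) will be fed and challenged as in task 2.1". It then fixes the sampling: "Ten mice/group will be anesthetized and sacrificed 7, 15, and 21 d.pi". Spleen and blood cells from the sacrificed mice are used for T-cell markers, and antibodies are measured by ELISA.

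The challenge it refers to is in Task 2.1, where mice are "intranasally challenged with a lethal dose of a Spanish SARS-CoV-2 D614G(S) isolate and followed for 3 weeks". Mortality is one of the outcomes there. The sample size paragraph under Task 2.1 says that the groups were sized "in order to detect a significant 45% change in survival".

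The sample size paragraph under Task 2.2 reads "Group size was calculated using Lehr's formula to have a power of 80" (per cent), "considering a 5% level of significance", for "a difference of 13 MFI in the CD4+ T cells between the two group means", "assuming a combined standard deviation of 10 MFI". Neither Task 2.2 nor that paragraph mentions expected survival, spare or replacement animals, how mice are assigned to a sacrifice day, or how mice that die early enter the comparisons.

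**The concern.** Ten mice at each of days 7, 15 and 21 makes 30, the whole group. The allocation works only if no mouse dies of the infection before its turn. Yet the dose is called lethal, the three-week follow-up in Task 2.1 covers the same 21 days, and Task 2.1 exists partly to see whether diet changes mortality.

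Two things follow. First, the stated power depends on a number of animals that the design does not secure. Second, if diet affects survival, the mice available after deaths begin have been selected differently in each diet group. A difference in T-cell markers or antibodies between diets may then reflect which mice lived rather than what the diet did to immunity. Adding animals would repair the first problem but not the second. The second matters because the objective that contains this task is to establish cause and effect between zinc levels and infection.

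**Working it through.** **Inputs from the documents.** Difference 13 MFI, SD 10 MFI, 5% significance, 80% power, Lehr's formula (Sample size, Task 2.2); 30 mice per group, ten per sacrifice day (Task 2.2); lethal dose and three weeks of follow-up (Task 2.1); 45% change in survival (Determination of sample size, Task 2.1). Sidedness is not stated; Lehr's constant of 16 corresponds to a two-sided 5% test. The 30 is read as per diet group, the only reading that fits ten per group on three days.

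**1. The plan's own figure.** Standardised difference 13/10 = 1.3. Lehr: n = 16/1.3² = 16/1.69 = 9.47, rounded up to 10 per group. The arithmetic reproduces. An exact t-test would need 10.34, so 11.

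**2. Power with n₁ and n₂ live mice.** Normal approximation: power = Φ(1.3/√(1/n₁ + 1/n₂) − 1.96). At 10 v 10: 1.3/√0.2 = 2.907, less 1.96 = 0.947, so 82.8%. The t-test figures use the same inputs with n₁ + n₂ − 2 degrees of freedom.

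**3. Assumed losses.** No survival rate by day is given, so these are scenarios.

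- The 45% change read as percentage points, with the better diet losing no mouse: 100% v 55%, so 10 v 10 × 0.55 = 5.5.
- The 45% change read as a relative increase, again with no loss in the better diet: 1/1.45 = 69%, so 10 v 6.9.

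| Live mice per group | t-test | Normal approximation |
|---|---|---|
| 10 v 10 | 78.5% | 82.8% |
| 10 v 9 | 76.0% | 80.8% |
| 9 v 9 | 73.5% | 78.7% |
| 10 v 6.9 (relative, best case) | 69% | 75% |
| 10 v 5.5 (points, best case) | 62% | 69% |
| 5.5 v 5.5 | 49% | 58% |

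Each column should be compared with its own 10 v 10 row. The last row has equal survival, so it shows lost numbers only, not selection by diet. If the better diet also loses mice, power falls further: at 75% v 30% survival (7.5 v 3 mice) the normal approximation gives 47.7%.

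**4. How little slack there is.** Even with 90% survival to the sampling day, the chance that all ten mice in one group are alive is 0.9¹⁰ = 35%.

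**5. Selection, as an illustration.** Suppose diet has no effect on the marker, survival is 65% v 20%, and marker and latent survival are normal with correlation ρ. The mean among survivors is shifted by 10ρφ(z)/p MFI, where p is survival and z its normal cut-point. For p = 0.20, φ(z)/p = 1.400; for p = 0.65 it is 0.570; the gap is 0.830. With ρ = 0.3 the survivors differ by about 2.5 MFI and with ρ = 0.5 by about 4.2 MFI, with no diet effect on the marker. The survival rates and ρ are assumptions; only the direction of the argument comes from the plan.

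**The case against.** The strongest reply is that the sample size is calculated correctly, that no survival curve is given, and that the loss may be small. Part of this stands. With 10 v 9 mice the plan's own approximation still gives 80.8%, so it would be too strong to say that the 80% cannot hold. What remains is that one death in each group takes power below 80% by either method, and a lethal dose makes more deaths than that likely.

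A reader might make five stronger inferences that the documents do not support:

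- **That at least one diet group will lose 45% or more of its mice.** The 45% is the change Task 2.1 is sized to detect, not a forecast of deaths, and it is not said to be absolute or relative. On the relative reading the worse group could lose about 31% (100 − 69).
- **That power fails just where memory and antibody responses are read.** Task 2.2 lists all markers together and ties none to a day. Only the patient study (Task 1.2.2) assigns memory to a time point.
- **That the plan treats survivors as a fair sample of each diet group.** It says nothing on the matter; the fault is an omission.
- **That day 7 is safe and can carry the 80% claim.** The documents do not say when deaths occur, so mice may be lost before day 7 too.
- **That these data are the main support for deliverable D3.** D3 concerns prophylaxis against severe disease, to which Task 2.1's survival and health scores speak more directly.

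It is also fair to say that this is a mouse subproject. No patient and no endpoint of the randomised trial is affected.

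**Conclusion.** The point holds as a gap between a stated property and the design. The 80% power in Task 2.2 is conditional on essentially every mouse being alive at its sampling day, and the plan does not say so. If the survival change that Task 2.1 is built to detect has appeared by the sampling day, power for those two diets is at most about 69% by t-test (75% by normal approximation) on the relative reading, or 62% (69%) on the percentage-point reading. Both are best cases in which the better diet loses no mouse. The true loss is unknown, because it depends on survival by day, which the documents do not give.

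The survivor problem does not depend on these figures. It needs only that mice die before sampling and that diet may change how many do, which Task 2.1 sets out to test. Importance is low for the trial as a whole, but the correction is cheap if made before animals are used.

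**What to change.** In Task 2.2 and its sample size paragraph:

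1. Assign each mouse at random to a sacrifice day before challenge, so that the day-15 and day-21 sets are not filled from whichever mice remain.
2. Report, for each diet and day, the number of mice assigned and the number alive at sampling.
3. Restate the 80% power as conditional on ten live mice per group at that day, and give power over a stated range of survival for each day, including day 7.
4. Label immune comparisons at any day with deaths before sampling (to be expected at days 15 and 21) as descriptive among survivors, not as causal effects of diet.
5. Reconcile the challenge described in Task 2.1 with the sampling schedule in Task 2.2.

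The cost is wording, with no extra animals; the downside is weaker claims at the later days. Challenging more mice is an alternative for the numbers only. Ten expected survivors per group and day would need 10/0.8 = 12.5, so 13, at 80% survival, or 10/0.5 = 20 at 50%. The selection by diet would remain.
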